4.1 Overall Design

The Study Schema is provided below in [Figure 3](#).

This is a Phase 1a/1b open-label, multicenter study to evaluate the dosing, safety, tolerability, PK, pharmacodynamics, and preliminary efficacy of FPA150 as monotherapy and in combination with pembrolizumab, an anti-PD1 antibody, in patients with advanced solid tumors.

There will be approximately 6 to 10 study centers participating in Phase 1a in the United States and approximately 35 study centers participating in Phase 1b. Phase 1a and the combination cohorts in Phase 1b will be conducted in the United States only. Phase 1b monotherapy will be conducted globally.

This study includes a Phase 1a FPA150 Monotherapy Dose Escalation, Phase 1a Monotherapy Dose Exploration, Phase 1a combination Safety Lead-in (FPA150 + pembrolizumab), a Phase 1b FPA150 Monotherapy Dose Expansion, and a Phase 1b combination Dose Expansion (FPA150 + pembrolizumab).

The Phase 1a Monotherapy Dose Escalation will include an initial accelerated titration design followed by a standard 3+3 dose escalation design until the MTD and/or RD for Phase 1b is determined. The Phase 1a combination Safety Lead-In will start enrolling once the FPA150 monotherapy RD is identified in Phase 1a monotherapy dose escalation and will continue until the FPA150 MTD/RD in combination is identified.

Phase 1a FPA150 monotherapy Dose Exploration may include cohorts that may enroll beyond 3 patients whose tumors express high levels of B7-H4 protein and/or have varying levels of B7H4 expression [REDACTED] to further evaluate safety, PK, pharmacodynamics, and clinical activity at that dose (to be conditional upon the dose level clearing DLT criteria)..

Phase 1b will be the Dose Expansion (monotherapy and combination) portion of the study. Enrollment into Phase 1b Dose Expansion will begin after identification of the MTD and/or RD in Phase 1a (monotherapy and Safety Lead-in). Preliminary efficacy will be evaluated in Phase 1b in planned expansion cohorts that include patients with specific tumor types that are B7-H4+ advanced solid tumors.

Archival tumor tissue or fresh biopsy requirements are as follows:**Required for all patients in Phase 1a Monotherapy Dose Escalation:**

- Provision of archival tumor tissue (or fresh biopsy if archival tissue is not available) for retrospective biomarker analysis for all patients

Required for all patients in Phase 1a Combination Safety Lead-in:

- Pre-screening of archival tumor tissue (or fresh biopsy required if archival tissue is not available) to evaluate for B7-H4 expression levels through IHC testing performed at a central laboratory and for retrospective biomarker analysis.

Required for all patients in Phase 1a Monotherapy Dose Exploration:

- Pre-screening test for B7-H4 expression levels through IHC testing and retrospective biomarker analysis will be performed at a central laboratory; fresh biopsy tissue will be required for this test if archival tissue is not available.
- Fresh biopsies mandatory during screening and on-treatment (prior to C3D1, please refer to [Appendix 2](#) for additional information).

Required for all patients in Phase 1b Monotherapy and Combination Dose Expansion:

- Pre-screening of archival tumor tissue to evaluate for B7-H4 expression level through IHC testing and retrospective biomarker analysis will be performed at a central laboratory; fresh biopsy tissue will be required for this test if archival tissue is not available.
- Fresh biopsies mandatory for a **subset of patients (at least 15 patients per 30-patient cohort)** during screening and on-treatment (prior to C3D1), for expanded pharmacodynamic analysis

Figure 3: Study Schema- Monotherapy

[figure not shown]
[figure not shown]

Figure 4: Study Schema - Combination

4.1.1 Cohort Review Committee

Safety will be monitored throughout the study by the Sponsor's Cohort Review Committee (CRC), consisting of at least the Sponsor's Medical Monitor, Safety Representative, and Study Investigators participating in Phase 1a. The CRC will meet routinely to review the emerging safety, PK, pharmacodynamics, and efficacy data, and to make dose escalation decisions. The CRC may recommend further evaluation of the safety at a given dose. The CRC will also review cumulative safety data in order to identify safety concerns that may emerge due to cumulative exposure beyond the DLT window. The process for dose escalation decisions and dose interval recommendations and the roles and responsibilities of the CRC will be detailed in the CRC Charter.

4.1.2 Study Design: Phase 1a Dose Escalation

Cohorts are planned at doses from 0.01 to 20 mg/kg, and enrollment will depend on safety and tolerability. Phase 1a Monotherapy Dose Escalation of the study will include an initial accelerated titration design followed by a standard 3+3 dose escalation design at dose levels ≥ 1 mg/kg until the MTD and/or RD for Phase 1b is determined. As of 28 January 2019, the RD for FPA150 monotherapy has been established as 20 mg/kg Q3W.

The proposed dosing cohorts are outlined in Table 3.

Table 3: Proposed Dose Levels for Phase 1a FPA150 Monotherapy

Dose Level	Cohort	Dose	Regimen
-1	-	FPA150 0.005 mg/kg	Q3W
1	1aM1	FPA150 0.01 mg/kg	Q3W
2	1aM2	FPA150 0.03 mg/kg	Q3W
3	1aM3	FPA150 0.1 mg/kg	Q3W
4	1aM4	FPA150 0.3 mg/kg	Q3W
5	1aM5	FPA150 1 mg/kg	Q3W
6	1aM6	FPA150 3 mg/kg	Q3W
7	1aM7	FPA150 10 mg/kg	Q3W
8	1aM8	FPA150 20 mg/kg	Q3W

Abbreviations: Q3W = once every 3 weeks.

4.1.2.1 Phase 1a Combination Safety Lead-in (Ovarian B7-H4⁺ Patients Only)

Once the MTD and/or RD of FPA150 monotherapy in Phase 1a Dose Escalation is identified, the Sponsor will open a Safety Lead-in for the combination of FPA150 and pembrolizumab. At least 3 patients will be enrolled at the monotherapy RD of FPA150 in combination with pembrolizumab 200 mg IV Q3W and evaluated for DLTs by the CRC. If required due to the presence of DLTs, the dose of FPA150 will be reduced in accordance with the algorithm for

de-escalation described in Table 4. The same dose levels that were assessed during dose escalation for FPA150 monotherapy will be evaluated for the combination in reverse order (from highest to lowest). Once the RD for the combination of FPA150 and pembrolizumab is identified the Sponsor may treat additional patients at that dose for additional safety assessment (up to 10 patients total).

Table 4: Proposed Dose Cohort/Levels for Phase 1a Combination Safety Lead-in (FPA150 in Combination with Pembrolizumab)

Cohort	Dose	Regimen
1aC1	FPA150 (RD) + pembrolizumab 200 mg IV	Q3W
1aC2	FPA150 (dose level -1) + pembrolizumab 200 mg IV	Q3W
1aC3	FPA150 (dose level -2) + pembrolizumab 200 mg IV	Q3W

Abbreviations: IV = intravenous; Q3W = once every 3 weeks; RD = recommended dose.

4.1.2.2 Definition of a Dose-Limiting Toxicity

4.1.2.2.1 FPA150 Monotherapy

DLTs during Phase 1a Dose Escalation are defined as any of the following events regardless of attribution (except for those events clearly due to the underlying disease or extraneous causes):

- Any Grade 3 or higher non-hematologic toxicity (except Grade 3 nausea, vomiting and diarrhea) occurring with the first 21 days of treatment
- Grade 3 nausea, vomiting, diarrhea lasting > 72 hours, despite optimal supportive care, occurring within first 21 days of treatment
- Febrile neutropenia and/or documented infection with absolute neutrophil count (ANC) < 1.0×10^9 per L, Grade 4 neutropenia lasting more than 7 days, Grade 4 thrombocytopenia (< 25.0×10^9 per L), or Grade 3 thrombocytopenia (< $50.0-25.0 \times 10^9$ per L) accompanied by bleeding within first 21 days of treatment
- Aspartate aminotransferase/alanine transaminase (AST/ALT) > 3 × upper limit of normal (ULN) and concurrent total bilirubin > 2 × ULN not related to liver involvement with cancer
- Other Grade 3 laboratory values that are not of clinical significance according to Investigator and Sponsor agreement that do not resolve within 72 hours
- Any Grade 4 laboratory value regardless of clinical sequelae

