Once the MTD and/or RD of FPA150 monotherapy is identified, the Sponsor will open a Safety Lead-in for the combination of FPA150 and pembrolizumab. At least 3 patients will be enrolled at the MTD and/or RD of FPA150 monotherapy combined with 200 mg pembrolizumab Q3W and evaluated for DLTs by the CRC. Once the RD for the combination is identified, the Sponsor may treat additional patients for a total of up to 10 patients treated at the RD of FPA150 + pembrolizumab. If required, the dose of FPA150 may be reduced in accordance with the algorithm for de-escalation described below. The proposed dose levels are:

Proposed Dose Cohort/Levels for Phase 1a Combination Safety Lead-in (FPA150 in Combination with Pembrolizumab)

Cohort	Dose	Regimen
1aC1	FPA150 (RD) + pembrolizumab 200 mg IV infusion	Q3W
1aC2	FPA150 (dose level -1) + pembrolizumab 200 mg IV infusion	Q3W
1aC3	FPA150 (dose level -2) + pembrolizumab 200 mg IV infusion	Q3W

Abbreviations: IV = intravenous; Q3W = once every 3 weeks; RD = recommended dose.

The de-escalation scheme will follow the same dose levels used in Phase 1a dose escalation. The Sponsor may evaluate lower or intermediate dose levels of FPA150 based on emerging safety data and in consultation CRC . The DLT criteria for the combination of FPA150 and pembrolizumab will be the same as those for FPA150 monotherapy, with the following additional considerations:

Additional DLT Considerations for FPA150 in combination with Pembrolizumab

Because pembrolizumab is a known immune checkpoint inhibitor and one of the proposed mechanisms of action of FPA150 is immune checkpoint blockade, immune-related adverse events (irAEs) are anticipated with this combination. An irAE is defined as a clinically significant AE that is associated with study drug exposure, of unknown etiology, and is consistent with an immune-mediated mechanism. Based on that background, the first occurrence of the following irAEs will not be considered a DLT because they are expected with immune therapy:

- Grade 3 tumor flare (defined as local pain, irritation, or rash localized at sites of known or suspected tumor)
- Grade 3 rash
- Grade 3 immune-related adverse event (irAE) that resolved to a Grade 1 or less within 14 days
- Transient (resolving within 6 hours of onset) Grade 3 infusion-related AE

A second occurrence of these events (except Grade 3 tumor flare) either in the same or different patient during the DLT window will be considered a DLT

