9.1 Sample Size Determination

For Phase 1a, this study is designed as a dose escalation study with objectives that include determination of an MTD and/or RD for FPA150 monotherapy and FPA150 combined with pembrolizumab. It will also include assessments of the safety and tolerability of FPA150 monotherapy and in combination with pembrolizumab. The sample size of this study was not determined by strict statistical considerations. The total number of patients planned for this study is estimated to be up to 278.

Phase 1a will enroll up to 68 patients. The 68 patients include 23 to 26 patients in the Phase 1a Monotherapy Dose Escalation cohorts, 6 to 22 patients in the Phase 1a Combination Safety Lead-in cohort and up to 20 additional patients in the Phase 1a Monotherapy Dose Exploration cohorts to further evaluate safety, PK, pharmacodynamics, and clinical activity at 1 or more dose levels (to be conditional upon the dose level clearing DLT criteria).

For the objective of estimating the ORR of FPA150 in the Phase 1b Monotherapy and Combination Dose Expansion cohorts, it is estimated that up to 30 patients will be enrolled to ensure 25 evaluable patients in each cohort. The following table displays the corresponding 2-sided 90% confidence interval (CI) and the precision for the various observed response rates based on 25 evaluable patients. The sample size of 25 is chosen to ensure that it will allow to exclude 10% when the observed ORR is 24% or higher ([Agresti 1998](#)).

Phase 1b will enroll up to 210 patients with specific tumor types. Up to 30 patients are planned for each of the 3 FPA150 Monotherapy Dose Expansion cohorts, and one additional cohort of FPA150 in combination with pembrolizumab. Additional cohorts of up to 30 patients each may be enrolled, based on emerging clinical and translational data.

Table 11: Two-Sided 90% Confidence Intervals of the Observed Response Rates

Sample Size	Observed Response Rate	90% CI	Precision (longest one-sided CI length*)
25	5/25 (20%)	(8%, 38%)	18%
	6/25 (24%)	(11%, 42%)	18%
	7/25 (28%)	(14%, 46%)	18%
	8/25 (32%)	(17%, 50%)	18%
	9/25 (36%)	(20%, 54%)	18%
	10/25 (40%)	(24%, 58%)	18%

Abbreviations: CI = confidence interval.

*Distance from the observed response rate to the lower or upper CI boundary.

Considering it is possible to open successive cohorts after data is reviewed, up to 210 patients may be enrolled in Phase 1b (not to exceed 30 patients in any individual cohort).

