APPENDIX 5: CLINICAL LABORATORY TESTS

The laboratory parameters outlined in Table 15 will be determined in accordance with the Schedule of Assessments and will be performed locally.

Table 15: Clinical Laboratory Tests

Hematology:	
Complete blood cell (CBC) with differential:	
white blood cells (WBC)	platelets
ANC	hemoglobin
neutrophils (%)	hematocrit
eosinophils (%)	red blood cells (RBC)
basophils (%)	
lymphocytes (%)	
monocytes (%)	
Urinalysis:	
Dipstick (appearance, color, pH, specific gravity, ketones, protein, glucose, bilirubin, nitrite, urobilinogen, and occult blood)	
If dipstick is positive (2+ or greater) for blood or protein, perform a microscopic examination.	
Clinical chemistry:	
Albumin	
alkaline phosphatase	glucose
ALT (SGPT)	lactate dehydrogenase (LDH)
AST (SGOT)	phosphate
blood urea nitrogen (BUN)	potassium
calcium	sodium
chloride	total bilirubin
carbon dioxide (CO ₂ [bicarbonate])	total cholesterol
creatinine	total protein
direct bilirubin	uric acid
magnesium	
Screening laboratory tests include: Serology for Hepatitis B (HBsAg and HBcAb), and Hepatitis C (HCV RNA)	
Serum pregnancy test: In women of childbearing potential only.	
Urine pregnancy test: In women of childbearing potential only.	
Coagulation: INR and APTT	

Abbreviations for [Table 11](#) and for notes: ADA = anti-drug antibodies; ALT = alanine transaminase; ANC = absolute neutrophil count; APTT = activated partial thromboplastin time; AST = aspartate transaminase; BUN = blood urea nitrogen; CBC = complete blood count; GGT = gamma-glutamyltransferase; HBcAb = hepatitis B core antibody; HBsAg = hepatitis B virus surface antigen; HCV = hepatitis C virus; INR = international normalized ratio; LDH = lactate dehydrogenase; PK = pharmacokinetics; RBC = red blood cell; RNA = ribonucleic acid; WBC = white blood cells.

Notes:

- Local hematology and blood chemistry test results must be obtained within 96 hours of dosing to confirm eligibility.
- If either AST or ALT is elevated, obtain total serum bilirubin and alkaline phosphatase; repeat daily or other interval, as clinically indicated, until resolved or stable.
- Additional tests to rule out drug-induced liver injury (eg, abdominal ultrasound, serum GGT, hepatitis serology) may be obtained at any time, if clinically indicated.

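### The DLT list counts a non-significant, persistent Grade 3 anemia or lymphopenia but not a clinically significant one

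*Protocol*

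**What the plan says.** Protocol 4.1.2.2.1 lists six DLT criteria, numbered here in the order of that section. The synopsis has the same six, with the last two swapped.

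1. "Any Grade 3 or higher non-hematologic toxicity (except Grade 3 nausea, vomiting and diarrhea"), within the first 21 days.
2. Grade 3 nausea, vomiting or diarrhea that persists beyond 72 hours.
3. Specified neutrophil and platelet events.
4. Raised transaminases together with raised bilirubin.
5. "Other Grade 3 laboratory values that are not of clinical significance according to Investigator and Sponsor agreement that do not resolve within 72 hours".
6. Any Grade 4 laboratory value.

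All six apply "regardless of attribution (except for those events clearly due to the underlying disease or extraneous causes").

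On the lead-in, the synopsis states: "The DLT criteria for the combination of FPA150 and pembrolizumab will be the same as those for FPA150 monotherapy". Section 4.1.2.2.2 adds a rule for immune-related events. A first Grade 3 event that resolves to Grade 1 or less within 14 days is exempt, and a second occurrence in any patient during the DLT period counts. Table 6 turns the DLT count in 3 or 6 patients into a decision to proceed or de-escalate. DLT incidence is a primary Phase 1a endpoint (Table 1), and SAP 7.1.7 summarizes DLTs as the protocol defines them.

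The counts at issue are measured: Appendix 5 specifies "Complete blood cell (CBC) with differential", which includes hemoglobin and lymphocytes.

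**The concern.** A toxicity rule should not count the milder form of an event and omit the more serious form. Bullet 5 does this for blood counts outside bullet 3, because it makes lack of clinical significance a condition for counting.

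The decision most exposed is the lead-in. On monotherapy the protocol says: "As of 28 January 2019, the RD for FPA150 monotherapy has been established as 20 mg/kg Q3W". What remains is "6 to 22 patients in the Phase 1a Combination Safety Lead-in cohort", in which FPA150 is first combined with a checkpoint inhibitor under the same criteria. Table 6 acts on very small counts, so one uncounted event can turn 1/3 into 0/3, or 2/6 into 1/6.

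**Working it through.** **Wording check.** Take a Grade 3 anemia that is clinically significant and not clearly due to disease. Bullet 1 excludes it as hematologic. Bullets 2, 3 and 4 concern other events. Bullet 6 needs Grade 4. Bullet 5 needs agreement that the value is not significant. Across the four possible states:

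| Grade 3 anemia or lymphopenia | Resolved within 72 h | Meets a listed bullet |
|---|---|---|
| Significant | Yes | No |
| Significant | No | No |
| Not significant | Yes | No |
| Not significant | No | Yes (bullet 5) |

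**Ways such an event can still count.**

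- Section 6.4.4 treats a required FPA150 dose reduction in the DLT period as a DLT. There is one dose per 21-day window, and Table 10 allows a first Grade 3 event to resume at full dose.
- Section 6.4.5 treats any dose modification for pembrolizumab-related toxicity in the lead-in as a DLT. It needs attribution to pembrolizumab.
- Section 4.1.2.2.2 counts a second occurrence of a resolving Grade 3 immune-related event in the lead-in.
- Bullet 1 counts a Grade 3 non-hematologic consequence of the low count.

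An anemia managed by transfusion or a stimulating agent (Section 6.10 allows the latter), with no dose change, no such consequence and no immune mechanism, takes none of these routes. The result is also uneven within the lead-in: a second resolving immune-mediated anemia counts, while a first one that fails to resolve meets no listed bullet.

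**Size.** The plan gives no operating characteristics for Table 6, so there is no stated figure to reproduce. Let p be the chance per patient of a counted DLT.

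P(proceed) = (1−p)³ + 3p(1−p)² × (1−p)³, and P(de-escalate) = 1 − P(proceed).

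As written p = b; after the fix p = b + q, taking the events as mutually exclusive and all counted. Both rates are assumptions: b = 5% or 10%, and q = 2% to 4.2%. The upper q is 1/24. Section 2.2.5.5 reports the most common Grade 3-4 term in 2 of 24 monotherapy patients, so if that term was strictly the most common, any other occurred in at most 1.

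Example, b = 5%: 0.857375 + 0.135375 × 0.857375 = 0.9734. With q = 2%, p = 7%: 0.804357 + 0.181629 × 0.804357 = 0.9505.

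| b | q | P(proceed) | P(de-escalate) | Rise (points) |
|---|---|---|---|---|
| 5% | 0 | 0.9734 | 2.7% | 0 |
| 5% | 2% | 0.9505 | 5.0% | 2.3 |
| 5% | 4.2% | 0.9195 | 8.1% | 5.4 |
| 10% | 0 | 0.9061 | 9.4% | 0 |
| 10% | 2% | 0.8715 | 12.9% | 3.5 |
| 10% | 4.2% | 0.8304 | 17.0% | 7.6 |

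Extra patients at a dose level before the decision = 3 × [P(1 of 3 at b+q) − P(1 of 3 at b)], where P(1 of 3) = 3p(1−p)². At b = 5%: 3 × (0.1816 − 0.1354) = 0.14 for q = 2%, and 3 × (0.2269 − 0.1354) = 0.27 for q = 4.2%. At b = 10%: 3 × (0.2788 − 0.2430) = 0.11, and 3 × (0.3131 − 0.2430) = 0.21.

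**The case against.** The omission may be deliberate. Bullet 3 already tolerates some Grade 3 cytopenias, such as thrombocytopenia without bleeding, so Grade 3 anemia or lymphopenia may not be meant to be dose-limiting. That is a reasonable position, but bullet 5 then wrongly counts the milder form. Either intent needs an edit.

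The formal count is also not the only safeguard. The synopsis says: "The Sponsor may evaluate lower or intermediate dose levels of FPA150 based on emerging safety data". The Cohort Review Committee may recommend further evaluation (4.1.1), dose escalation decisions weigh overall safety (4.1.2.3), and selection of the recommended dose considers toxicity outside the DLT criteria (4.1.2.4). This stands: patients need not be left unprotected. It does not repair the count or the endpoint. Nor is the SAP at fault, since it is not expected to correct a protocol definition.

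The immune-related exemption would still keep some first events uncounted after the fix, so p = b + q overstates the change. The anchor for q is weak too. It covers all Grade 3-4 terms over a median exposure of 63 days on monotherapy, Section 2.2.5.5 names no anemia case, and the only Grade 3 treatment-related event it reports is hypertension. Both points stand, so the figures are illustrative only.

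**Conclusion.** The rule is wrong as written for significant Grade 3 hematologic values outside bullet 3. This follows from the text and needs no assumed rate. Its effect is confined to the formal Table 6 count and the DLT-incidence endpoint, for events that take none of the four routes. Under the assumed rates, the probability of de-escalation is understated by 2.3 to 7.6 points, and by less where the immune-related exemption applies.

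Three stronger readings are tempting but unsupported:

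- A reader might infer that a significant Grade 3 anemia can never be a DLT. The four routes contradict that.
- A reader might extend the gap to all Grade 3 laboratory values. Bullet 1 can catch a significant non-hematologic value, and bullet 3 addresses neutrophils and platelets.
- A reader might conclude that the monotherapy dose is unsound, or that the effect is much larger. Section 2.2.5 reports no DLTs and names no uncounted anemia. Taking q as high as 2/24 (8.3%) would give rises of 12.7 points at b = 5% and 16.2 at b = 10%, but the documents do not anchor that rate for so narrow an event. Nor would these be upper limits: the same formula gives 18.0 points at b = 20%.

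The point is worth fixing because the error is in the definition of a primary endpoint and the repair is short.

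**What to change.** Amend Section 4.1.2.2.1 and the synopsis as follows.

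- Leave neutrophils and platelets wholly to bullet 3 and the Grade 4 bullet.
- For other Grade 3 hematologic values, count a DLT when the Investigator and Sponsor agree that the value is clinically significant, for example when it requires transfusion, other treatment or a dose delay.
- State that extra monitoring alone does not qualify. Section 8.5 treats a result that prompts monitoring as significant, and Table 12 schedules safety laboratory tests only on Day 8 between the first two doses. The 72-hour recheck will usually be unscheduled and could itself make a value significant.
- Apply the 72-hour rule for non-significant values only where the significant state also counts. If a count such as lymphocytes is not meant to be dose-limiting, exempt it in both states.
- State that the first-occurrence exemption in 4.1.2.2.2 still applies in the lead-in.

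The cost is a protocol amendment with ethics approval (Section 10.8). No new procedures are needed: blood counts are already scheduled and transfusions are already recorded (Section 8.13). Slightly more events would count as DLTs, adding about 0.1 to 0.3 patients per dose level before the decision under the assumed rates. Events clearly due to disease stay excluded, which matters because patients may enter with hemoglobin as low as 9.0 g/dL.
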